**Document date: Thursday December 12, 2024**

## Research Approach

We will achieve our aims by having 200 non-smoking adolescents (aged 15-16) complete a laboratory study (Figure 2). During their visit, Adolescents will then be randomly assigned to watch a smoking movie that manipulates exposure to ENDS Advertisements. Attention to movie smoking will be measured using validated eye movement measures of attention. Adolescents will then complete SC-IAT task to measure how exposure to ENDS ads affected their implicit smoking expectancies and implicit normative beliefs.

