## Primary Measures

**Implicit measurement of positive smoking expectancies and social normative beliefs about smoking using the SC-IAT.** A modified version of the SC-IAT will be administered before and after exposure to ENDS ads. The SC-IAT is a validated implicit association computer task that can be used to measure the associations between a visual cue (e.g., a smoking-related image) and a) personal implicit attitudes (e.g., implicit positive smoking expectancies)

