
**ENDS ad and control exposure.** Immediately following the first SC-IAT,

adolescents will view a 15-minute movie clip that manipulates exposure to ENDS ads. ENDS ad exposure will be manipulated by embedding naturally occurring commercial breaks at 5 and 10 minutes. During each break, adolescents in the ENDS ad exposure condition will view ENDS ads for 30 seconds each. The commercial break will also include 3 30-sec control ads (e.g., food, clothes, and cars) to disguise the purpose of the experiment. Adolescents in the control ad condition will view 4 minutes of control commercials at each break. ENDS and control ads will be randomly sampled from the 8 most popular brands in the United States in 2016.

**Attention to dynamic smoking cues.** Dynamic smoking cues are any action that promotes or represents a smoking behavior. Selective attention is an implicit measure of cue saliency that is defined as an automatic response to attend to an environmental stimulus. Measuring eye movements to dynamic cues has been shown to be a validated measure of selective attention to smoking cues in movies. Eye tracking will be recorded using the Gazepoint GP3 eye-tracker (Vancouver, British Columbia). The GP3 device has a sample rate of 60 Hz and an accuracy of 0.5 to 1 degree of visual angle.

**Covariate Assessment.** We will measure the following covariates because they have been associated with tobacco advertising exposure and adolescent smoking, but are not thought to part of the causal pathway. We will collect sociodemographic factors including age, gender, and socioeconomic status. Socioeconomic status will be measured using the validated three item index of the Programme for International Student Assessment. We will also measure social influences on smoking using validated questions, including the smoking status of parents and the smoking status of peers. Rebelliousness and sensation seeking will be assessed using a validated 4-item index because it has been strongly associated with adolescent smoking intuition. Following our laboratory's previous work, we will also measure long-term exposure to on screen movie smoking using a validated method.

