## Primary analysis plan

Our outcomes of interest are as follows: 1) Implicit positive vaping expectancy scores measured post-intervention, and 2) selective attention to dynamic smoking cues. To assess the effect of ENDS advertising on implicit attitudes, we will use linear regression to predict Implicit positive vaping expectancy scores from advertising condition. We also use linear regression to assess the association between the amount of attention given to dynamic smoking cues and Implicit positive vaping expectancy scores. Specially, Implicit positive vaping expectancy scores will be predicted from dynamic attention scores in the onscreen smoking experimental arm. For all analyses, we will first calculate appropriate summary statistics, assess normality, and transform the data if necessary. We will include potential covariates in all analyses when they are significantly associated with the outcome ( $P < 0.05$ ). We will conduct all analyses in the full sample stratified by sex, and conduct formal tests for interactions using a Wald Test on sex by exposure multiplicative interaction terms in full models.

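### The pre-exposure SC-IAT score is collected but has no place in the analysis; it should be a pre-specified covariate in both regressions, with a fixed covariate set replacing the P<0.05 screen

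*Combined protocol and SAP*

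**What the plan says.** The Research Approach section of the combined protocol and SAP plans for "200 non-smoking adolescents (aged 15-16) complete a laboratory study". It randomises advertising only: "Adolescents will then be randomly assigned to watch a smoking movie that manipulates exposure to ENDS Advertisements". Attention is then measured by eye tracking; it is not assigned.

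Under Primary Measures, the SC-IAT "will be administered before and after exposure to ENDS ads". The paragraph on ad and control exposure starts the movie "Immediately following the first SC-IAT". So the first score precedes both the advertisements and the attention measurement. The SC-IAT has a personalised phase (expectancies) and a social phase (normative beliefs), and both are described in terms of smoking.

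The Covariate Assessment paragraph justifies its list on prior grounds: "We will measure the following covariates because they have been associated with tobacco advertising exposure and adolescent smoking". The list is age, gender, socioeconomic status, parent smoking, peer smoking, rebelliousness/sensation seeking and long-term movie-smoking exposure. The pre-exposure SC-IAT score is not on it.

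The Primary analysis plan takes the post-intervention score for positive *vaping* expectancies and regresses it on ad condition. In a second model, "Implicit positive vaping expectancy scores will be predicted from dynamic attention scores in the onscreen smoking experimental arm". Its covariate rule is "We will include potential covariates in all analyses when they are significantly associated with the outcome", at P<0.05. Sex interactions use a "Wald Test on sex by exposure multiplicative interaction terms in full models", and the full models are not defined.

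**The concern.** A baseline measurement of the outcome is often its best single predictor. Here it is already collected, and it cannot lie on the pathway from attention to the post score because it comes first. Leaving it out has a different consequence in each model.

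- **Randomised ad comparison.** The estimate stays unbiased, but the standard error is larger than it need be.
- **Attention regression.** Adolescents who already hold positive expectancies may look more at smoking cues and also score higher afterwards. If so, the attention slope partly reflects what they brought to the laboratory.

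The P<0.05 rule adds a smaller difficulty. It admits a covariate on its relation to the outcome alone and ignores its relation to attention. A non-significant test in 100 to 200 people does not show that a covariate is not a confounder.

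**Working it through.** The plan gives no power calculation, standard deviation or correlation, so there is no stated figure to reproduce.

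**Inputs.** From the documents: 200 participants, ad condition randomised, seven listed covariates, screen at P<0.05. Assumed: 1:1 allocation, two-sided tests, a univariable screen, and every correlation below. The attention model has n=100 if the undefined *onscreen smoking* arm is one ad arm, or n=200 if it is everyone who watches the movie.

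**1. Randomised comparison: precision.** Adding a pre score that correlates r with the post score multiplies the standard error by about √(1−r²).

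- r=0.3: √0.91 = 0.954, about 5% smaller.
- r=0.5: √0.75 = 0.866, about 13% smaller.

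If the seven listed covariates are mutually independent and each correlates 0.15 with the outcome, they explain 7×0.0225 = 0.1575. The multiplier is then √[(0.8425−r²)/0.8425]: √(0.7525/0.8425) = 0.945 for r=0.3 and √(0.5925/0.8425) = 0.839 for r=0.5. Simulated ratios for the fixed set against the screen at n=200 were also 0.945 and 0.839. False positives were 4.9-5.0% with the screen and 4.8-5.2% with the fixed set, so type I error is not an issue here.

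**2. Attention regression: pre score left out.** Suppose attention has no effect once the pre score is known. The attention-post correlation is then the product r(pre, attention) × r(pre, post). By Fisher's z, the rejection rate is Φ(d−1.96) + Φ(−d−1.96), with d = atanh(product) × √(n−3).

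Example, n=100, product 0.3×0.5 = 0.15: d = 0.1511×√97 = 1.489; Φ(−0.471) = 0.319; the other tail is negligible. Result: 31.9%.

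| r(pre, post) | r(pre, attention) | Product | n=100, formula | n=100, simulation |
|---|---|---|---|---|
| 0.3 | 0.1 | 0.03 | 6.0% | 6.0% |
| 0.3 | 0.2 | 0.06 | 9.1% | 9.0% |
| 0.3 | 0.3 | 0.09 | 14.4% | 14.4% |
| 0.5 | 0.1 | 0.05 | 7.8% | 7.9% |
| 0.5 | 0.2 | 0.10 | 16.7% | 16.4% |
| 0.5 | 0.3 | 0.15 | 31.9% | 31.8% |

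At n=200 with r(pre, post)=0.5, the formula gives 10.8/29.1/56.4% and simulation 11.0/28.8/56.2%. (Simulations of the attention model: multivariate normal, 40,000 replicates per cell.) With the pre score plus the seven listed covariates the rate is 4.8-5.2%. With the seven listed covariates forced in but no pre score, at n=100 and r(pre, post)=0.5, it is 7.7/15.9/30.3%. Removing the screen alone therefore does not cure this.

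**3. What the screen does by itself.** By the same formula, a confounder with r=0.15 with the outcome passes the screen 32% of the time at n=100, 56% at n=200 and 18% at n=50 (one arm, one sex). At n=100 it is dropped about two times in three. Resulting false positives for the attention slope at n=100:

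- One to four independent confounders, r=0.15 with both attention and score: 5.1, 5.4, 5.9 and 6.5%.
- All seven confounding in the same direction, r=0.10/0.15/0.20: 6.7/11.4/17.7% if mutually independent, but 4.9/5.1/4.7% if they correlate 0.2 with each other.
- Three same-direction confounders, r=0.3-0.4 with attention but 0.15 with the score: 9.2-12.4% if independent, 6.0-6.8% if they correlate 0.2.
- Mixed signs (3,000 replicates): seven at r=0.15, four positive and three negative, 4.5%; the three strong ones with one sign flipped, 4.7% and 5.0%. A separate mixed-sign run gave 4.6% and 6.2%.

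**The case against.** A reader might infer that the P<0.05 screen itself inflates error to 30% or more, or that it undermines the randomised result. Neither follows. The large rates come from a score missing from the covariate list, not from the threshold. If the pre-exposure score were offered to the screen at n=100, it would be kept in 86% (r=0.3) to 100% (r=0.5) of trials, and the false-positive rate would be 4.9-5.2%. The plan also does not exclude the score: the rule speaks of potential covariates, so an analyst could put it forward. But nothing commits anyone to do so.

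Three further defences have weight.

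- Attention is itself named as an outcome. If the rule admits a covariate related to either outcome, the three-confounder case disappears (4.9% and 4.1%, against 8.6% and 11.5% in the same runs). The rule refers to a single outcome, so this is the less natural reading, but the text does not rule it out.
- Forcing covariates in reduces bias but raises variance. Combining the two approximately at n=100, total error for screen against forced set is 0.107 v 0.105 with four confounders, and 0.121 v 0.119 and 0.139 v 0.140 with three strong ones. These are near ties. The forced set is clearly better only with seven independent same-direction confounders (0.124 v 0.105).
- The plan calls the attention analysis an association. That limits the causal claim, but an association explained by prior expectancy would still be of little use.

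What stands is the unused baseline score. The case against the screen stands only as a modest one.

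**Conclusion.** The point holds, as a recommended change, with medium confidence. Its main part is the pre-exposure score. Including it gives a precision gain in the randomised comparison: about 5% off the standard error at r(pre, post)=0.3 and 13-16% at 0.5. It also guards against bias in the attention regression, where leaving it out gives about 6-14% or 8-32% false positives at n=100, against about 5%.

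These sizes rest on assumed correlations. If the pre score is unrelated to attention, the attention slope is not biased by its omission.

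The screen is secondary. Its own harm is usually about 5-7% false positives. It is larger only when several nearly independent confounders act in the same direction, and it largely disappears with mixed signs or with correlation of about 0.2 among the covariates. The documents do not support a claim that the screen invalidates either analysis.

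**What to change.** **Main change.** Pre-specify the pre-exposure SC-IAT score from the personalised (expectancy) phase as a covariate in both the ad comparison and the attention regression. It must measure the same construct as the outcome. So first reconcile the smoking expectancies described under Primary Measures with the vaping expectancies named in the Primary analysis plan.

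**Secondary change.** Replace the P<0.05 rule with one fixed set: that score plus the seven covariates in Covariate Assessment. State whether the attention model uses one ad arm or everyone, and add ad condition if it pools both. Use the same set in the sex-interaction models, without gender inside sex strata. Keep any screened model as a labelled sensitivity analysis.

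**Cost.** SAP wording and no new data. For the attention slope, compared with screening:

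- Forcing in the seven listed covariates makes the standard error about 4-7% larger at n=100, 1-4% at n=200, and 9-12% at n=50 within a sex stratum (six covariates).
- It is 15-30% larger at n=100 if three covariates relate strongly to attention.
- A prognostic pre score offsets this. With listed covariates unrelated to attention and score, the full set of eight at n=100 gives a standard error 0-5% larger if r(pre, post)=0.3 and 4-9% smaller if 0.5.
- If the pre score does not predict the outcome, the standard error is about 8% larger (listed covariates at r=0.15).
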